6.2.3.1.1 Exploratory endpoints

For all exploratory time-to-event endpoints, randomization baseline will be used for all the analyses unless otherwise specified. Week 24 baseline will not be defined for exploratory endpoints.

Radiological endpoints

Only central reviewer assessments will be analyzed for exploratory radiological endpoints.

Time to radiological bone progression is defined for each comparison as the time (days) from randomization date to the date of confirmed radiological bone progression. See [Table 9–5](#) in Appendix [9.1.4](#) for detailed censoring rules.

Time to radiological soft-tissue progression is defined as the time (days) from randomization date to the date of radiological soft tissue progression. See [Table 9–5](#) in Appendix [9.1.4](#) for detailed censoring rules.

Quantitated bone scan endpoints

Digitized images of whole body quantified technetium-99 bone scans will be evaluated by the central imaging reviewer using CAD system software using the method of Brown et al. (2012) [8], as described in the imaging charter. The central reviewer will use the CAD system software to evaluate each subject’s digitized whole body quantified technetium-99 scans at each timepoint. The reviewer will identify the bone pixels, and determine the area (cm²) and disease status (bone lesion, not bone lesion) associated with each bone pixel [8].

The analysis timepoints for the analysis of quantitative bone scan endpoints are randomization baseline, Week 8, 16, 24, and every 12 weeks thereafter.

For analyses reported by visit, nominal visit per CRF will be used.

Patient bone scan lesion area (BSLA) is defined for each subject at each assessment as the sum of the pixel areas (cm²) of the set of the whole body quantified technetium-99 bone scan imaging pixels identified as bone lesion, as determined by the central imaging reviewer using the CAD system software.

Patient bone scan timepoint response rate (week 8, 16 and week 24) For each comparison, patient bone scan timepoint response with respect to the randomization baseline will be assessed according to the following criteria in [Table 6–2](#):

Table 6–2 Patient Bone Scan Timepoint Response Criteria Following Randomization

Responder (R)	30% or greater resolution of the BSLA compared to baseline
Stable Disease (SD)	Not meeting the criteria for R, PD, or UE
Progressive Disease (PD)	Two or more new areas of radiotracer uptake attributable to metastatic disease in regions of bone that had not previously shown radiotracer uptake or greater than 30% increase from baseline in bone scan lesion area in areas attributable to metastatic disease.
Unable to Evaluate (UE)	Assigned if bone scan results cannot be interpreted due to inconsistent image acquisition parameters compared to the reference scan, incomplete imaging, or other similar technical deficiencies.

Subjects with no randomization baseline assessment or a baseline BSLA value of 0 will be assigned ‘UE’ values for all timepoints for the comparison. The response rate is the proportion of subjects with a response at the timepoint among the subjects evaluable for bone scan response at the randomization baseline.

Patient bone scan best overall response rate is defined for each comparison as the proportion of subjects having the best bone scan timepoint overall response as R, SD, PD, or UE among subjects with a non-zero BSLA measurement at the randomization baseline. Overall response is judged on all responses observed during the post-baseline period, including unscheduled visits. Responder and SD responses will only be reported if observed prior to PD. No confirmation of R or PD status is required.

Total ALP and PSA Endpoints

Total ALP and PSA endpoints are determined based on the total ALP and PSA laboratory assessments collected as described in the schedule of procedures.

Total ALP response rate is defined as the proportion of subjects with a $\geq 30\%$ reduction of the blood total-ALP level compared to the randomization baseline, confirmed by a second consecutive ALP value 4 or more weeks later but within 9 weeks, among evaluable subjects.

PSA response rate is defined as the proportion of subjects with a $\geq 30\%$ reduction of the blood PSA level, compared to the randomization baseline value, confirmed by a second consecutive PSA value 4 or more weeks later but within 9 weeks, among evaluable subjects.

In addition, **percentage change from randomization baseline in Total ALP** at weeks 12 and 24 will be summarized for Comparison 1.

Time to total ALP progression is defined as the time (days) from randomization date to the date of first total ALP progression. A progression event is defined as $\geq 25\%$ increase from randomization baseline value, at least 12 weeks from baseline in subjects with no ALP decline from baseline; or $\geq 25\%$ increase above the nadir value, which is confirmed by a second consecutive value obtained 3 or more weeks later but within 9 weeks in subjects with an initial ALP decline from the baseline.

Time to total ALP progression without 12-week restriction is similar to the time to total ALP progression defined above except that 12-week rule is removed in subjects with no ALP decline from baseline.

See [Table 9–4](#) in Appendix [9.1.3](#) for detailed censoring rules.

Time to PSA progression is defined as the time (days) from randomization baseline to the date of first PSA progression. A progression event is defined as $\geq 25\%$ increase from randomization baseline value and an increase in absolute value of ≥ 2 ng/mL, at least 12 weeks from the applicable baseline in subjects with no PSA decline from baseline; or $\geq 25\%$ increase and an absolute increase of ≥ 2 ng/mL above the nadir value, which is confirmed by a second consecutive value obtained 3 or more weeks later but within 9 weeks in subjects with an initial PSA decline from the baseline.

Time to PSA progression without 12 week restriction is similar to the time to PSA progression defined above except that 12-week rule is removed in subjects with no PSA decline from baseline.

See

Table 9–4 in Appendix 9.1.3 for detailed censoring rules .

Analgesic Use and Related Endpoints

Analgesic use in this study will be captured via two methods:

- Analgesic concomitant medication case report form, where the physician records the analgesic medication prescribed to manage pain.
- 24 hour analgesic consumption case report form, in which all analgesic medication taken in the last 24 hours.

Data from both sources will be used to identify strength of each analgesic used by each subject at baseline and post-baseline visits. The amount of medication a subject actually took cannot be calculated due to only prescribed information is collected on the eCRF. Hence, only drug name will be used in identifying non-, weak- or strong- opioids for analgesics related analyses.

Analgesic names will be coded into standard terms using the World Health Organization Drug Dictionary (WHO-DD), Version 2005 Q3.

Each standardized analgesic name will be classified by strength type as non-opioid, weak opioid, or strong opioid.

An increase in analgesic use following randomization baseline is defined in Table 6–3 below. If a subject is using more than one type of analgesic, the strongest type will be used in the analysis.

Table 6–3 Increase in Analgesic Use Algorithm

Baseline intake	Post baseline
No analgesics or a non-opioid	Initiation of any opioid
Weak opioid	Initiation of any strong opioid or adding an additional weak opioid
Strong opioid	Initiation of an additional strong opioid

Pain improvement rate without increase in analgesic use following baseline is defined at each post-baseline assessment time point as the proportion of subjects with a 30% and 2-point decrease in average WPS over 2 consecutive assessment periods conducted at least 4 weeks apart, without a corresponding increase in analgesic use over those 2 periods. The denominator is the number of subjects with a non-missing WPS of at least 4 at randomization.

Time to increase in analgesic use is defined as the time in days from randomization baseline until the first increase in analgesic use for subjects with baseline average WPS of ≤ 7 and non-missing baseline assessment of analgesic use. See Table 9–5 in Appendix 9.1.4 for detailed censoring rules.

Pain progression or increase in analgesic use following baseline is defined as the time in days from randomization baseline until the earlier of pain progression or a first increase in analgesic use for subjects with a non-missing baseline average WPS of ≤ 7 . See [Table 9–4](#) in [Appendix 9.1.3](#) for detailed censoring rules.

Change in analgesic use following baseline : A shift table will be presented to summarize the change in strength of analgesic use from randomization baseline to the strongest use at post-baseline. The strength type will include: no analgesics or non-opioid, weak opioid, and strong opioid.

NCCN-FACT FPSI-17 Endpoints

The NCCN-FACT FPSI-17 is a validated instrument that was developed to assess symptoms of prostate cancer, symptoms caused by the treatment of prostate cancer, and the health related quality of life of prostate cancer patients. [12] The instrument contains 17 items, each of which utilizes a Likert scale with 5 possible responses. Ten items reflect disease related physical symptoms of disease and the responses on the items are to be summed to calculate a disease related physical symptom subscale score (FPSI-DRS-P, Disease Related Symptoms – Physical), One item represents emotional symptoms of disease and the response to that item is used to calculate a disease related emotional symptom subscale score (FPSI-DRS-E, Disease Related Symptoms – Emotional). Four items represent treatment related symptoms and the responses to these items are summed to calculate a treatment side effect subscale score (FPSI-TSE, Treatment Side Effects). Finally, two items represent functional well-being and the responses to those items are summed to calculate a functional/well-being subscale score (FPSI-F/WB, Function/Well Being).

The NCCN-FACT FPSI-17 total score and each of its subscale scores, FPSI-DRS-P, FPSI-DRS-E, FPSI-TSE, and FPSI-F/WB, will be summarized by visit.

Time to increase in physical symptoms of disease based on FPSI-DRS-P will be evaluated based on the FPSI-DRS-P subscale score of the NCCN-FACT, as the time from treatment start to the first increase in physical symptoms of disease on-study. NCCN-FACT FPSI-17 was not collected prior to randomization, so baseline is the assessment collected prior to first dosing. An increase is defined as a 2 point drop in DRS-P score that persists for two consecutive assessments at least 4 weeks apart, if two consecutive assessment are available. If there is a 2 point drop in the DRS-P score and the next assessment is not available due to death then that single 2 point drop would count as a deterioration. See [Table 9–4](#) in [Appendix 9.1.3](#) for detailed censoring rules.

BPI Subscales

Each subject will fill out the complete 11-question BPI-SF using an ePRO device at the Treatment Day 1 visit and at each clinic visit thereafter through Week 48. For subjects in Arm A and Arm B, the modified complete BPI-SF will also be filled out on the day of telephone contacts scheduled for Weeks 28, 32, 40, and 44. The data will be collected for one week (6 days prior to the applicable visit and the morning of the visit) prior to each clinic visit or phone call follow-up.

The BPI-SF (Protocol Section 14.9) is a short, self-administered questionnaire with 11 items, which was designed to evaluate the intensity of, and the impairment caused by pain. All BPI-SF items are scored using rating scales. Four items measure pain intensity (pain now, average pain, worst pain, and least pain) using 0 (“no pain”) to 10 (“pain as bad as you can imagine”) numeric rating scales, and seven items measure the level of interference with function caused by pain (general activity, mood, walking ability, normal work, relations with other people, sleep and enjoyment of life) using 0 (no interference) to 10 (complete interference) rating scales.

The items are aggregated into two dimensions, (1) **Pain severity index**, using the sum of the four items on the pain intensity, and (2) **Function interference index**, using the sum of the seven pain interference items (at least 4 out of 7).

Each BPI-SF subscale, and the two indices for pain severity and function interference, will be summarized using descriptive statistics.

Weekly Average pain score (APS) is defined for each subject at baseline and at each post-baseline date, as the mean of the “average pain score” values in the last 24 hours from the preceding 7 days before each applicable visit or telephone contact per the BPI-SF.

Analysis of Exploratory Endpoints

Identical statistical methods for analyzing time-to-event secondary endpoints, as elucidated in section 6.2.2.2, will be applied to the analysis of time-to-event exploratory endpoints:

- Time to radiological bone progression
- Time to radiological soft-tissue progression
- Time to total alkaline phosphatase (ALP) progression
- Time to ALP progression without 12-week restriction
- Time to PSA progression
- Time to PSA progression without 12-week restriction
- Time to pain progression or increase in analgesic use following baseline
- Time to increase in analgesic use
- Time to increase in physical symptoms of disease based on FPSI-DRS-P

Descriptive statistics (n, nmiss, mean, std, median, interquartile range, range) will apply to other exploratory endpoints by timepoint:

- Bone scan lesion area
- Percent change in ALP from baseline
- NCCN-FACT FPSI-17 subscale scores and total score
- BPI-SF subscales and 2 indices (pain severity and function interference)

The following rates will be summarized using (n, %) with exact binomial 80% and 95% CIs using the method of Clopper and Pearson [7]

- Timepoint and Best overall bone scan response rate

- ALP response rate
- PSA response rate
- Pain improvement rate without increase in analgesic use
 - Plots with 80% and 95% confidence intervals at each timepoint will also be provided.

A shift table will be presented to summarize the change in the strength of analgesic use from randomization baseline to the strongest use at post-baseline.

Summary statistics on weekly worst pain score at baseline and at each post-baseline timepoint (n, nmiss, mean, std, median interquartile range, range) will be presented.

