6.2 Efficacy

For Comparison 1, Arm A will be pooled with Arm C in the time-to-event analyses. Refer to censoring rules in Section 4.5 for the pooling algorithm. No pooling of Arm C subjects will occur in Comparison 1 for non-time-to-event endpoints (e.g. pain improvement rate).

As sensitivity analyses, the analyses described for Comparison 1 will also be performed between Arm A and Arm B only (i.e., without pooling Arm C data).

Each efficacy endpoint will be defined separately for Comparison 1 and Comparison 2. For Comparison 1 analyses, endpoints will be defined following randomization baseline. For Comparison 2 analyses, endpoints will be defined following Week 24 baseline (the 6th dose date) unless otherwise specified.

Imaging endpoints based on tumor assessments, will not follow the Week-24 baseline for Comparison 2 analyses. The study did not plan to do Week 24 re-baseline for the site investigators. The site investigators would determine PD only based on the randomization baseline. Once a subject had a PD (or a confirmed PD for bone progression) based on randomization baseline, the subject will not be further followed for a second PD using Week-24 assessment as the new baseline. Therefore, there will be no assessments after an observation of PD to perform re-reads of tumor assessments based on the Week-24 baseline by the central reviewer. This incomplete tumor assessments can lead to a biased analysis favoring one arm vs the other (i.e., the arm with more PDs based on randomization baseline could have more censored data for the analyses based on Week-24 baseline). Hence, the Comparison 2 analysis on the Week-24 population will only be performed based on the randomization baseline, not the Week-24 baseline for both investigator and centrally reviewed data.

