No event by database cutoff	Last assessment prior to	Yes	No Event

	database cutoff		
--	-----------------	--	--

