9.1.4 Censoring rules for time to radiological progression

Note: ‘radiological’ in the tables refer to either ‘radiological soft tissue’ or ‘radiological bone’ as applicable to the endpoint.

Refer to Section 4.5.2 for pooling cut-off date.

Table 9–5 applies to:

- **Time to radiological progression following randomization**
- **Time to radiological bone progression following randomization and**
- **Time to radiological soft tissue progression following randomization.**

The following censoring rules will be used for both Comparison 1 and Comparison 2. Randomization baseline is used for all comparisons.

Table 9–5 Censoring for Time to Radiological Bone/Soft Tissue Progression following randomization

Situation	End Date	Censored	Reason for Censoring
No randomization baseline or post-randomization baseline radiological assessment	Date of randomization	Yes	No baseline or post-baseline assessment.
Subject died without prior radiological progression	Date of last radiological assessment before death	Yes	No progression before death or database cutoff
Subject survived without radiological progression as of database cutoff date	Date of last radiological assessment before data cutoff	Yes	Alive and no progression before database cutoff
Subject had a radiological assessment of PD (no two consecutive missed radiological assessments*)	Date of first PD	No	N/A
PD immediately after two or more consecutive missed radiological assessments*	Date of last radiological assessment before missed assessments	Yes	Missed two or more consecutive tumor assessments
Subject discontinuation from study for reasons other than PD	Last radiological assessment date	Yes	Subject discontinued from study due to a reason other than PD
Subjects discontinued from study due to PD, but no documented date of PD	Date of last radiological assessment	Yes	Subjects discontinued from study due to PD, but no documented date of PD
New non-protocol permitted systemic anti-cancer treatment started	Date of last radiological assessment before starting new systemic anti-cancer treatment	Yes	New anti-cancer treatment started

*Two consecutive missing radiological assessments are defined as the time interval between two consecutive radiological assessments is more than 28 weeks = $2 \times (12+2)$ week, where 12-week is scheduled frequency for tumor assessment and 2-week is protocol-allowed window.

Duration = End date – randomization date +1

There will be no Week 24 baseline censoring for Comparison 2.

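### Best overall bone-scan response has no stop at a new systemic anti-cancer treatment, so a fall in lesion area on the next drug can count as a radium-223 response; PSA and ALP response lack the same stop

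*SAP*

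**What the plan says.** SAP section 6.2.3.1.1 defines best overall bone-scan response from centrally read lesion area. A responder has at least a 30% reduction from the randomization baseline (Table 6-2). Three sentences fix which scans count:

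- The first sets the period: "Overall response is judged on all responses observed during the post-baseline period, including unscheduled visits".
- The second sets the only stop: a response or stable disease counts when it was seen before bone-scan progression.
- The third makes a single scan sufficient: "No confirmation of R or PD status is required".

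The same section schedules the quantitative scans at Weeks 8, 16 and 24 and then every 12 weeks. The separate timepoint response rate is limited to Weeks 8, 16 and 24.

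PSA response is a reduction of at least 30% "compared to the randomization baseline value, confirmed by a second consecutive PSA value 4 or more weeks later" and within 9 weeks; ALP response is built the same way. Neither definition names an end of the assessment period, a stop at progression or a stop at new treatment. The sampling times are left to the schedule of procedures.

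The radiological time-to-event endpoints do have a rule. When a new systemic anti-cancer treatment not permitted by the protocol is started, Table 9-5 (section 9.1.4) sets the end date to "Date of last radiological assessment before starting new systemic anti-cancer treatment". Table 9-7 (section 9.1.5) does the same for rPFS.

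**The concern.** Time to radiological bone progression and best overall bone-scan response both come from central review of bone scans. After a switch to a new treatment, a scan no longer counts as evidence of progression but still counts as evidence of response. The SAP gives no reason for the difference and does not say that response is meant to be counted regardless of later treatment.

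The exploratory objectives in section 2 include determining bone tumor response and evaluating laboratory indicators of efficacy. A rate that includes responses to the next drug serves these objectives less well. It could also differ between arms for reasons unrelated to radium-223 if subjects in one arm switch earlier, or are assessed longer after switching.

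**Working it through.** The SAP gives no expected response rate, power or switching rate for these endpoints, so there is no planned figure to reproduce. The check is a comparison of the rules, followed by an illustration on assumed inputs.

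**Rules side by side**

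| Endpoint | Assessments that count | Stop at progression | Stop at new treatment |
|---|---|---|---|
| Time to radiological progression (including bone), rPFS | until event or censoring | is the event | yes (Tables 9-5, 9-7) |
| Best overall bone-scan response | all post-baseline, unscheduled included | yes, bone-scan PD | none |
| Timepoint bone-scan response | Weeks 8, 16, 24 | not stated | none |
| PSA and ALP response | not stated; schedule of procedures | none | none |

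**Does the scan schedule outlast dosing?** Dosing is every 4 weeks (section 1). With no delays, dose 6 falls at 5 × 4 = Week 20 and dose 12 at 11 × 4 = Week 44, which agrees with the 44 weeks used in section 3.4. The gap is 44 − 20 = 24 weeks. Scans at Weeks 24 and 36 therefore fall after the last dose in Arms A and B but within the dosing period of Arm C. From Week 48 all arms are past the last dose.

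**Who is exposed?** Only a subject who has had no bone-scan PD, starts a new treatment, is still scanned, and then shows at least a 30% reduction from the randomization baseline. One such scan is enough.

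**Illustration (all inputs assumed).** Let p be the response rate before any new treatment. Let s be the share of the remaining subjects who start a new treatment without earlier bone-scan PD and have a later scan. Let q be the response rate to the new treatment among them.

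Counted rate = p + (1 − p) × s × q, so inflation = (1 − p) × s × q.

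With p = 20%:

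| s | q = 20% | q = 50% |
|---|---|---|
| 0 | 0 | 0 |
| 10% | 0.80 × 0.10 × 0.20 = 1.6 points | 0.80 × 0.10 × 0.50 = 4.0 points |
| 30% | 0.80 × 0.30 × 0.20 = 4.8 points | 0.80 × 0.30 × 0.50 = 12.0 points |
| 50% | 0.80 × 0.50 × 0.20 = 8.0 points | 0.80 × 0.50 × 0.50 = 20.0 points |

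For two arms with the same p and q, the spurious difference is (1 − p) × q × (difference in s). It is 0 if s is equal. If s is 30% in one arm and 10% in the other, it is 0.80 × 0.20 × 0.20 = 3.2 points to 0.80 × 0.50 × 0.20 = 8.0 points. The arm with more post-switch scans gets the higher rate.

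Because s already excludes subjects with earlier bone-scan PD, the upper rows need many switches without such PD. The SAP does not indicate whether that is likely.

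**The case against.** Several points on the other side stand.

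- **The PD stop is substantial.** A single scan with two new areas of uptake, or an increase in lesion area of more than 30%, ends eligibility for R. Section 6.2 also expects imaging to cease at progression: "there will be no assessments after an observation of PD to perform re-reads of tumor assessments". This narrows the problem, but it does not reach subjects who switch without PD.
- **A reader might infer that all bone-scan, PSA and ALP responses are counted over the whole post-baseline period.** The SAP does not say so. The sentence on all post-baseline responses governs best overall bone-scan response only. Timepoint response is fixed at three visits up to Week 24. The PSA and ALP period is left to a schedule not shown; if sampling ends at or near the end of treatment, there is little or nothing to inflate.
- **Comparison 1 is largely protected from a difference between arms.** Section 6.2 does not pool Arm C for endpoints that are not time-to-event, so response rates compare Arms A and B, which have the same number and spacing of doses.
- **Earlier switching in Arm A is plausible, not documented.** Both SAP supplements foresee concomitant abiraterone and enzalutamide, so other active treatment is not confined to the time after the last dose.
- **Counting all data regardless of later treatment can be a legitimate choice.** It should then be stated, and it sits oddly beside Tables 9-5 and 9-7.

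A reader might also infer that Table 9-4 needs a new-treatment row for PSA and ALP progression, since a subject without progression is followed until "No event by database cutoff". That does not follow. SSE-FS, OS, time to first SSE and time to pain progression have no such rule either, so Table 9-4 agrees with most of the plan. Censoring at a switch that rising markers may have prompted would probably be informative.

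**Conclusion.** The gap is real for best overall bone-scan response: followed as written, the SAP can credit a response on a later drug to the randomized arm. For PSA and ALP response the stop is equally absent, but the exposure cannot be judged without the sampling schedule.

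The size is unknown. The 0 to 20 points for the rate, and the 3.2 to 8.0 points between arms at a 20-point difference in switching, rest wholly on assumed p, s and q. They show how the bias scales and do not predict it. The concern about a difference between arms applies mainly to Comparison 2.

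A stronger conclusion, that these rates cannot serve as indicators of radium-223 activity, is not supported: no switching rate is given and the PD stop removes part of the exposure. The rates are exploratory and are summarized as counts, percentages and exact confidence intervals without a test. The co-primary SSE-FS analyses and the secondary endpoints are untouched. This is an inexpensive improvement rather than a flaw in the main conclusions.

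**What to change.** In section 6.2.3.1.1, count best overall bone-scan response, PSA response and ALP response only from assessments made before the first new systemic anti-cancer treatment that the protocol does not permit, using the same start date as Tables 9-5 and 9-7. Keep a subject without a response by that date in the denominator as a non-responder for the response rate. Report the current all-data version as a sensitivity analysis. Leave Table 9-4 unchanged.

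The cost is a few lines of SAP text and one date filter, and the date is already needed for rPFS. The downside is somewhat lower response rates in the main presentation; the sensitivity analysis shows by how much.
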